Intrathecal Morphine versus Bilateral Quadratus Lumborum Blocks for Perioperative Analgesia in Pediatric Patients Undergoing Open Lower Abdominal Procedures: A Prospective Randomized Trial

NCT05506930

July 13, 2023

PROTOCOL TITLE:

Intrathecal Morphine versus Bilateral Quadratus Lumborum Blocks for Perioperative Analgesia in Pediatric Patients Undergoing Open Lower Abdominal Procedures: A Prospective Randomized Trial

PRINCIPAL INVESTIGATOR:

[name].

- **Objectives / Specific Aims**

- We hypothesize that intrathecal morphine will have superior analgesia as demonstrated by charted pain scores and morphine equivalents in the first 24 hours.
- We hypothesize that intrathecal morphine will have higher incidence of side effects when compared to quadratus lumborum blocks

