10.0 Study Design / Methods

- This prospective, randomized, blinded study will attempt to determine if intrathecal morphine provides superior analgesia postoperatively for open lower abdominal procedures when compared to bilateral quadratus lumborum blocks. It will also assess side effects of both pain interventions.
- Once a parent/guardian provide written informed consent, subjects will be assigned a number with a corresponding group. Randomization will be performed by a statistician prior to enrollment and assigned based on the patient's enrollment number. Subjects will be assigned to one of the following groups: 1) Intrathecal Morphine: spinal (neuraxial) dose of preservative free morphine (duramorph), usually about 4-5mcg/kg, or 2) Quadratus Lumborum Block: peripheral nerve block utilizing ropivacaine 0.2%, usually about $\frac{1}{2}$ mL per kg per side (total dose approximately 1mL/kg). The total dose of administered medication (duramorph or ropivacaine) is at the discretion of the anesthesiologist but will be within the dose range as stated above.
- The operating room pharmacist will follow the randomization to prepare or provide the correct medication. Intrathecal morphine will be prepared by the operating room pharmacist. Local anesthetic vials for quadratus lumborum blocks will be obtained from the pharmacy and the medication will be drawn into a syringe by an anesthesiologist who is part of the research team prior to injection. The dosage prepared and administered will be based on weight.
- The pharmacist will not be blinded to the randomization. Nor will the operative team. The study team member who completes data collection from the family and chart review will be blinded to randomization. In addition, the parent and child will also be blinded to the type of block that is used.
- The intervention will be administered in the operating room after the subject is under general anesthesia but prior to incision, as per usual practice. The block will be performed by a study team member board certified in pediatric anesthesiology. Quadratus lumborum blocks are placed using ultrasound guidance, local anesthetic is injected in the fascial plane using aseptic technique. Intrathecal morphine is accomplished by injection of preservative-free morphine in the intrathecal space in the lumbar region using sterile technique.

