12.0 Data Management

- All data will be kept on a password protected MUSC server and in a REDCap database. All paper data sheets will be kept in a locked cabinet, in a locked office that only IRB approved study team members have access to. Participants will be given a study ID number that will be used to identify them throughout the study.
- The primary outcome of interest is duration of analgesia as demonstrated by morphine equivalents per kg of body weight given in the first 24 hours after surgery.
- Secondary outcomes observed include charted pain scores and reported side effects such as nausea/vomiting or pruritis in the first 48 hours as well as patient/family satisfaction, sedation, length of hospital stay, length of PACU stay, and analgesia for hospital stay, the numerical value for SPO2, SPO2 trend, and use or lack thereof of supplemental O2 in PACU in 15-minute intervals for up to two hours after arrival there.

Demographic and clinical characteristics will be described and compared across the two groups using appropriate statistical tests (Chi-squared tests of homogeneity for categorical variables and t-tests for equality of means, etc.). Significant covariates will be assessed for inclusion in modeling. General linear regression methods will be

used to assess the association of post-surgery MMEs with group (QL vs ITM) adjusted for associated covariates.

Our primary hypothesis is that subjects in the two groups will consume different amounts of post-surgery MMEs. Based on preliminary data from a similar study, we assume that MME/kg consumption in the QL block group will be 0.07 ± 0.076 .

Summary Statements

Assuming a normal underlying distribution, group sample sizes of 12 and 12 achieve 80% power to detect a difference of 0.1 MME/kg between the null hypothesis that both group means are 0.07 and the alternative hypothesis that the mean of group 2 is 0.17 with known group standard deviation of 0.076 and with a significance level (alpha) of 0.05000 using a two-sided Mann-Whitney test. As we anticipate a non-normal distribution, we will inflate sample size by 15%. We will inflate the sample size further by 10% to account for withdrawals.

The final inflated sample size will be 15 per group.

Two-tail test that QL < ITM

$H_0 = \text{Mean}_{QL} = \text{Mean}_{ITM}$

$H_a = \text{Mean}_{QL} \neq \text{Mean}_{ITM}$

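### The only power calculation assumes intrathecal morphine patients use more opioid, the opposite of the benefit the trial sets out to show

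*Combined protocol and SAP*

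**What the plan says.** The expected direction appears twice. The opening statement of the trial's aims reads: "We hypothesize that intrathecal morphine will have superior analgesia as demonstrated by charted pain scores and morphine equivalents in the first 24 hours". Section 10.0 says the study will try to "determine if intrathecal morphine provides superior analgesia postoperatively".

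The sample size is justified once, in Section 12.0 Data Management:

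- From preliminary data, "we assume that MME/kg consumption in the QL block group will be 0.07", with an SD of 0.076.
- Under the null both means are 0.07. The power is computed for "the alternative hypothesis that the mean of group 2 is 0.17 with known group standard deviation of 0.076", a difference of 0.1 MME/kg, with 12 per group, 80% power and a two-sided Mann-Whitney test at 0.05.
- Allowances of 15% for expected non-normality and 10% for withdrawals bring this to 15 per group.
- The formal hypotheses are equal versus unequal means, in line with "Our primary hypothesis is that subjects in the two groups will consume different amounts of post-surgery MMEs". The line above them reads "Two-tail test that QL < ITM".

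Section 12.0 does not say which arm is group 2. Section 10.0 lists ITM as 1) and QL as 2): "or 2) Quadratus Lumborum Block: peripheral nerve block utilizing ropivacaine 0.2"%.

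**The concern.** The primary outcome is opioid given per kg in the 24 hours after surgery, so better analgesia means a lower value. With QL at 0.07 and the other arm at 0.17, the calculation describes ITM doing worse, and the direction line agrees with that reading. The Objectives and Section 10.0 say the opposite. The intrathecal dose itself does not explain the higher figure: it is given before incision, and the outcome counts opioid given after surgery.

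Consumption cannot be negative, so the 0.1 difference cannot simply be turned round. This is the only basis for the sample size. If 0.07 really is the QL mean, a null result could be reported as coming from a trial with 80% power when the power for a moderate ITM benefit is far lower. If the labels were swapped, the power stands, but the protocol names the wrong arm and the wrong direction.

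**Working it through.** **Inputs (Section 12.0).** Mean 0.07 and SD 0.076 for QL; alternative mean 0.17; difference 0.10; two-sided alpha 0.05; 12 per group, inflated to 15.

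**1. The plan's own figure reproduces.**

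- Normal approximation: n = 2(1.960 + 0.842)² × 0.076² / 0.10² = 9.07, so 10 per group.
- With 12 per group, power is 89.7% (normal approximation), 86.8% (t-test) and 84% (simulated Mann-Whitney, normal data).
- If the t-test is discounted by the worst-case Mann-Whitney efficiency of 0.864, power is 77.1% at 11 and 81.0% at 12 per group. Twelve is the first size to reach 80%.
- Inflation: 12 × 1.15 × 1.10 = 15.2, or 12 × 1.15 / 0.90 = 15.3, consistent with 15.

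The arithmetic is sound. The direction is the problem.

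**2. Reverse the direction with QL at 0.07.** 0.07 - 0.10 = -0.03, which is impossible for a consumption. The largest conceivable reduction is 0.07.

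**3. Power for attainable reductions, SD held at 0.076, normal data, 15 per group.**

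| ITM reduction | Normal approx. | t-test | Mann-Whitney (simulated) | n per group for 80% (normal approx.) |
|---|---|---|---|---|
| 0.07 (to zero) | 71% | 68% | 65% | 19 |
| 0.035 (halving) | 24% | 23% | 21% | 75 |

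An unchanged SD close to zero consumption is unrealistic, so these figures are only indicative.

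**4. SD allowed to fall with the mean.** Assumption: constant coefficient of variation, CV = 0.076 / 0.07 = 1.086. Gamma shape = 1/CV² = 0.848; lognormal log-SD = √ln(1 + CV²) = 0.882. Exact two-sided Mann-Whitney, 40,000 replicates per cell. Evaluable after 10% withdrawals: 15 × 0.9 = 13.5, taken as 13.

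| Scenario | 15 per group, gamma to lognormal | 13 per group, gamma to lognormal |
|---|---|---|
| QL 0.07, ITM 0.035 (halving) | 28% to 51% | 24% to 44% |
| QL 0.07, ITM 0.014 (80% reduction) | 87% to 99.6% | 82% to 99% |
| Reduction at which power reaches about 80% | 76% to 62% | 79% to 65% |

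**5. If the labels were swapped (ITM 0.07, QL 0.17).**

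- Normal data, equal SD 0.076: about 92% at 15 and 86% at 13 per group, so the claim of 80% is met.
- SD scaling with the mean (0.17 × 1.086 = 0.185): 42% (gamma) to 72% (lognormal) at 15; 37% to 64% at 13.

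**6. Group numbering.** On the order in Section 10.0, group 2 is QL, so 0.17 would be QL. That fits the expected direction but contradicts both the QL figure of 0.07 and the direction line in Section 12.0. No reading satisfies all three sections.

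**The case against.** The best defence is that the test is two-sided and the primary hypothesis in Section 12.0 is non-directional. Under the stated normal model with equal SD, the power for a 0.1 difference is the same either way, and 0.17 versus 0.07 lies inside the formal alternative. The plan never proposes a negative mean; that appears only when the effect is reversed. All of this is right. The validity of the test, the type I error and the arithmetic are not in question. But a two-sided test does not make a 0.1 benefit attainable from 0.07, so the stated power still says nothing about the effect the trial expects.

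The numbering point is weak by itself. The 1) and 2) in Section 10.0 may be mere list markers, and Section 12.0 is internally consistent if group 2 is ITM. The conflict with the Objectives and with the aim in Section 10.0 remains without it.

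The power figures depend on assumptions and are not bounds:

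- Section 12.0 plans linear regression for the analysis. An unadjusted t-test at 15 per group gives 33% (gamma) to 41% (lognormal) for a halving, and 49% to 60% for 0.17 versus 0.07 with scaled SD.
- If 20% to 30% of children receive no opioid (an assumption, with the same mean and SD and gamma otherwise), Mann-Whitney power for an 80% reduction falls to about 63% to 51%.

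These variants change the sizes but do not remove the contradiction.

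On the SD, the plan does state a normality assumption and adds 15% for departures from it. What it leaves unstated is that 0.076 is also assumed for the second arm.

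**Conclusion.** The concern holds. The sole power statement assumes an effect in the direction opposite to the trial's stated expectation, and its 0.1 difference cannot occur as a reduction from 0.07. This is an inconsistency of direction, not a miscalculation: 12 and 15 per group follow from the inputs.

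Whether power is lost depends on which arm the preliminary 0.07 describes:

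- **0.07 is QL.** At 15 per group, power for a halving is about 28% to 51% under a constant CV, or 21% if the SD stays at 0.076 (Mann-Whitney in each case). Under a constant CV, 80% power needs a reduction of about 62% (lognormal) to 76% (gamma).
- **0.07 is ITM and QL is 0.17.** The stated 80% stands under normal data with equal SD, but not if the SD grows with the mean (42% to 72% at 15 per group).

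The SD already exceeds the mean and the plan itself expects non-normal data, so the equal-SD assumption deserves a sensitivity figure in either case.

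**What to change.** Go back to the preliminary data, establish which arm the 0.07 came from, and reconcile the Objectives, Section 10.0 and Section 12.0.

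- If 0.07 is ITM and QL is 0.17: correct the arm label and the direction line. The stated power can then stay, conditional on equal SDs.
- If 0.07 is QL: restate the power at 15 per group, and at about 13 evaluable, for ITM reductions smaller than 0.07, with an SD that depends on the mean and a range across plausible distributions.

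In both cases, say which arm is group 2, declare the common SD of 0.076 as an assumption with a sensitivity figure, and replace the direction line with a two-sided test whose expected direction matches the Objectives.

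The cost is protocol wording only, with no extra patients. The possible downside is a less favourable stated power if 0.07 does belong to QL.

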13.0 Data Safety Monitoring

- The study will be reviewed annually by the Department of Anesthesia's DSBM. Minutes and outcomes from these meetings will be reported to the IRB as required.
- Adverse events will be recorded and reported to the Department of Anesthesia's Data Safety Monitoring Board and the IRB per policy.
- PHI will be managed in a manner that complies with institutional rules and regulations. There will be an enrollment log that links the study ID number to the patient. This log will be kept on a MUSC password protected server that can only be accessed by IRB approved study personnel.

14.0 Withdrawal of Subjects

- If the anesthesiologist is unable to complete the regional anesthesia administration the patient will be withdrawn from the study.
- If at any time the parent wishes to be withdrawn from the study, then the patient will be withdrawn. This can occur preoperatively or postoperatively when the parent is contacted by the research team approximately 24 hours after surgery. Any data collected prior to withdrawing will be retained.

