- Approximately 24 hours after the procedure, a research team member will ask the parent/guardian about side effects such as nausea, vomiting, itching, etc. The research team member will also ask the family if they were satisfied with the subject's pain control postoperatively and overall experience. If a family member or guardian is not present, a care team member will be asked about side effects and the patient's chart will be reviewed for notes pertaining to side effects.
- The patient's chart will be used to see if and how much narcotic pain medication was administered in the first 48 hours after the procedure as well as documented pain scores up to 48 hours after the procedure ends. The chart medication administration record will also be used to identify administration of rescue medications for nausea

or itching non-opioid medications such as acetaminophen or ibuprofen, or other medications such as diazepam or oxybutynin.

Table 1. Baseline and Intraoperative Assessments	
Demographics	
Baseline	
Pre-op meds including opioids in past 24 hours	
Randomization	
Anesthesia intra-op data	
Surgical techniques	
Adverse Events	

Table 2. Post-Op Follow Up Assessments		
Outcome Measure	Instrument	Collected
Pain Scores	Charted pain scores	24 and 48 hrs. post-op
Pain Control Satisfaction	Parent/Guardian Satisfaction	24-hours post-op
Side Effects Experienced	Parent/Guardian Satisfaction	24-hours post-op
Overall Satisfaction	Parent/Guardian Satisfaction	24-hours post-op
Opioid Consumption	MME Consumption	24 and 48 hrs. post-op
Side Effects and Adverse Events	Adverse Events	Assessed through post-op hours 0-48
Medications	Medications used to control or relieve side effects	24 and 48 hrs. post-op

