15.0 Risks to Subjects

- If a parent chooses for their child not to participate, the risk is the same since regional anesthesia is part of standard care at MUSC and will be offered regardless of study participation. Both study medications have been routinely used in practice at MUSC for over ten years.
- Subjects will be assigned to receive intrathecal morphine or a quadratus lumborum block by chance. One group may prove to be less beneficial than the other.
- Intrathecal Duramorph/Morphine: the use is well established in pediatric patients even though it is not FDA approved for use in children, but is commonly used in this population and at this institution for this indication. Other risks include infection at site of injection (less than 1%), damage to surrounding structures (less than 1%), block failure (1%) headache and cerebral spinal fluid leak (7%), Urinary retention (6%), Nausea and vomiting are the most common risks/side effects occurring in less than 10% of patients. Itching occurs in 20-40% of patients. Literature states that patients recover from side effects and are not long term.

QL Block/Ropivacaine: complications/risks are rare but include local anesthetic systemic toxicity (less than 0.01%), block failure (1%), bleeding and infection at block site (less than 1%), damage to surrounding structures (less than 1%), allergic reaction (rare, less than 1%), neurological complications (less than 1%). Literature states that patients recover from side effects and are not long term.

- There is a risk of loss of confidentiality.

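### Withdrawing randomised children whose assigned block cannot be completed, with no analysis population named, turns the trial into a comparison of completed blocks

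*Combined protocol and SAP*

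**What the plan says.** Section 10.0 assigns a group once the parent or guardian has consented. The block comes later: "The intervention will be administered in the operating room after the subject is under general anesthesia but prior to incision". On who knows the allocation, the same section says: "The pharmacist will not be blinded to the randomization. Nor will the operative team". The child, the parent and the data collector are blinded.

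The first bullet of Section 14.0 reads: "If the anesthesiologist is unable to complete the regional anesthesia administration the patient will be withdrawn from the study". The second bullet deals with withdrawal at the parent's wish and ends: "Any data collected prior to withdrawing will be retained".

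Section 12.0 makes MME/kg over the 24 hours following surgery the primary outcome and plans a linear regression on group. It names no analysis population and gives no rule for missing outcomes. It does say: "We will inflate the sample size further by 10% to account for withdrawals".

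The outcome source is the chart. Section 10.0 has it reviewed for "how much narcotic pain medication was administered in the first 48 hours after the procedure" and for pain scores over the same period.

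**The concern.** The rule removes a child because of something that happens after assignment and that may depend on the technique assigned: one lumbar intrathecal injection in one arm, two ultrasound-guided flank injections in the other. An operator who knows the allocation decides whether the block was completed. Blocks that are given but do not work stay in; only uncompleted ones go.

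If those children are left out, the children remaining in each arm were selected by a process that can differ between arms, and the comparison is no longer the randomised one. The direction of any bias cannot be known in advance. The plan does not say what analgesia such a child receives. The nearest statement, about families who decline the study, is that "regional anesthesia is part of standard care at MUSC and will be offered regardless of study participation".

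The exclusion is also avoidable. No consent has been withdrawn in this situation, and the child's opioid use and pain scores will be in the chart regardless.

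**Working it through.** **The plan's own figure.** The inputs in Section 12.0 are a difference of 0.1 MME/kg, SD 0.076, two-sided alpha 0.05, Mann-Whitney test, 80% power and 12 per group.

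- Taking the lower-bound relative efficiency of 0.864 for the Mann-Whitney test, power is 77.1% at 11 per group and 81.0% at 12, so 12 is reproduced.
- Simulation under normality gives 84–85% at 12.
- Inflation: 12 × 1.15 × 1.10 = 15.2, against the stated 15.

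The sample size is therefore not in dispute.

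**Does a retained outcome exist?** The order of events is consent, assignment, anesthesia, block attempt, incision, surgery, then the 24-hour outcome window. A child withdrawn at the block attempt has only baseline data. Even if the data-retention sentence in the second bullet of Section 14.0 is stretched to cover this case, it retains no primary outcome.

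**How often might it happen?** The documents give no non-completion rate. Section 15.0 lists 1% block failure for each technique. That may describe an ineffective block rather than an uncompleted one, so it is only a stand-in, and the higher rates below are assumptions. With rate p:

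- P(at least one of 30) = 1 − (1 − p)^30
- P(two or more in a given arm of 15) = 1 − (1 − p)^15 − 15p(1 − p)^14

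| p | Expected of 30 | At least 1 of 30 | 2 or more in a given arm |
|---|---|---|---|
| 1% | 0.3 | 26.0% | 1.0% |
| 3% | 0.9 | 59.9% | 7.3% |
| 5% | 1.5 | 78.5% | 17.1% |
| 10% | 3.0 | 95.8% | 45.1% |

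**How far does one exclusion move an arm?** If the child would have differed from the rest of the arm by d, leaving the child out shifts the arm mean by d/15. The values of d are assumptions, in either direction.

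- d = 0.05: 0.0033 MME/kg, 3% of the 0.1 target
- d = 0.1: 0.0067 MME/kg, 7%
- d = 0.2: 0.0133 MME/kg, 13%

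The standard error of the difference with 15 per arm is 0.076 × √(2/15) = 0.0278. For d = 0.1 the shift is 0.0067/0.0278 = 0.24 standard errors.

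**Expected net bias.** With the same d in both arms, its size is (p1 − p2) × d.

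- Equal rates: 0
- 5% versus 1%: 0.04 × 0.1 = 0.004 to 0.04 × 0.2 = 0.008 MME/kg (4–8% of the target)
- 10% versus 1%: 0.09 × 0.1 = 0.009 to 0.09 × 0.2 = 0.018 MME/kg (9–18% of the target)

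**The case against.** **The exclusion is inferred.** Nowhere does the plan say that withdrawn children are left out of the analysis, and the chart review is not made conditional on a completed block. The section numbering also runs from 10.0 to 12.0, so one cannot be sure that nothing is missing. This stands as a caveat. Yet a child withdrawn from the study, under a sample size that budgets for withdrawals, is most naturally read as lost to the analysis. If the sponsor means otherwise, the same sentences are still needed.

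**The effect is probably small.** At 1% in both arms the chance of no such child is 74% and the expected net bias is zero. Even with 1% in one arm and none in the other it would be 0.01 × 0.1 = 0.001 to 0.01 × 0.2 = 0.002 MME/kg, or 1–2% of the target. Experienced operators, ultrasound guidance for the flank blocks and the spinal exclusions all point to a low rate. This stands, and nothing in the documents supports 10% versus 1%.

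**The operator cannot be blinded.** True. The event also precedes every outcome, so the decision cannot be driven by outcomes. It can still differ by technique, which is enough to unbalance the arms.

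**It is a choice of estimand.** The stated purpose is to compare the analgesia the two techniques provide. If a child with an uncompleted block received the other technique, keeping that child in the assigned arm could move its mean by 0.1/15 = 0.0067 MME/kg at the target difference, as much as the exclusion shift above. That is a real cost in dilution. It belongs to the effect of assignment, however, which randomisation protects, and the completed-block comparison can still be reported beside it.

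**Power.** If the 15% reserve for non-normality is kept, 12 × 1.15 = 13.8, so 14 per arm, and only one child per arm can be lost before the reserve is touched, parental withdrawals included. Still, 12 per arm meets the plan's stated 80%, and this point does not rest on power.

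**Conclusion.** The concern holds. As written, the plan removes randomised children after assignment because the assigned technique was not delivered, at a time when they have no outcome to retain, and it names no as-randomised population to bring them back. Followed literally, it compares completed blocks.

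The likely bias is small if non-completion is rare and similar in both arms, and its sign is unknown. It becomes material only if the rates differ clearly between techniques or if two or more children are lost from one arm of 15. All the sizes rest on assumed non-completion rates and assumed differences in opioid use. The point should be corrected because the remedy is cheap and because, in a trial of 30, the choice of analysis set should not be left until outcomes are known.

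**What to change.** In Section 14.0, replace the first bullet with wording such as: *A randomised child in whom the assigned block cannot be completed stays in follow-up. The 24-hour and 48-hour chart data and the 24-hour interview are collected unless the parent withdraws consent.*

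In Section 12.0, add: *The primary analysis includes all randomised children in their assigned group. The number of uncompleted blocks and the reasons are reported by arm, and a comparison restricted to completed blocks is given as a sensitivity analysis.*

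This concerns data collection and analysis only and leaves the child's care unaddressed. It needs no additional subjects, visits or instruments: the chart data will exist and the interview is already planned. The sponsor should check that the consent wording permits continued data collection; the consent pages were not available for this review. The statistical cost is some dilution of the contrast by uncompleted blocks, which the sensitivity analysis would show.
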